Group Mg (Study group) patients will receive 40 mg/kg of magnesium sulphate loading in 30 minutes at incision and then continuous drip 10 mg/kg/hr until dura will be closure. Group NSS (Control group) patients will receive normal saline with the same amount for loading and continuous infusion. Identical infusion syringes of magnesium (Mg) and placebo will be prepared and labeled by the research staff that will not provide care for the patients.

Anesthesia will be maintained with sevoflurane not exceeding 1 minimal alveolar concentration (MAC) with supplemental of intermittent fentanyl 0.5-1 mcg/kg, and continuous cis-atracurium 0.06-0.1 mg/kg/hr. If the depth of anesthesia is not adequate, propofol 2-6 mg/kg/hr continuous will be given.

Hematocrit levels will be measured every 2-3 hours. Intraoperative transfusion triggered for packed red cell is a hematocrit < 27%. Magnesium level will be measured at beginning and 4 hours. If magnesium level is more than 4 mg/dl, study drug will be stopped. Intraoperative bleeding will be measured by collection in suction bottle, plastic bags, drapes, and soaked gauzes subtracting the amount of irrigating fluid.

After the uneventful operation, the patients will be extubated and transferred to neurosurgical intensive care unit. Some patients will remain intubation and post-operative ventilation will be continued and reasons for remaining intubation will be noted.

Postoperative cognitive function test (MOCA) will be done at postoperative day 3-7 when patient has less pain and recover enough for comfortable testing.

The measure outcomes are intraoperative blood loss, amount of pack red cell (PRC) transfusion requirement, anesthetic requirement and postoperative MOCA score.

Study Protocol

The effects of magnesium sulphate on intraoperative blood loss in meningioma patient undergoing craniotomy with tumor removal: A prospective randomized study.

Special equipment preparation

1. Equipment for arterial line insertion for continuous BP monitoring
(A-line may be not required, according to anesthesiologist in charge)
2. Two syringe pumps for study drug and muscle relaxant administration
3. Study drug (be prepared by investigator)
4. Two heparin tubes (green capped tube)
5. Equipment for hematocrit assessment

Monitoring & IV access

- Standard monitoring (NIBP, Pulse oximetry, EKG, End tidal CO₂)
- Arterial line insertion (before or after induction)

Induction

- **Fentanyl 1-2 mcg/kg**
- **Propofol 1.5-2 mg/kg**

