- **Cis-atracurium 0.15 mg/kg** then wait for 4 minutes before intubation
- Use Sevoflurane in Air:Oxygen 1:1, Sevoflurane < 1 MAC
- Positioning as usual
- Aspirate blood from A-line **3 ml** into heparin tube for assess baseline Mg level
(Aspirate from vein if no A-line)

Maintenance

- Prepare study drug in syringe pump
- At skin incision **Study drug 0.2 ml/kg loading drip in 30 minutes** for example BW 60 kg use drug $0.2 \times 60 = 12$ ml drip 24 ml/hr for 30 minutes then IV continuous **0.05 ml/kg/hr** for example BW 60 kg administer 3 ml/hr
- Use **Cis-atracurium IV continuous infusion 0.06-0.1 ml/kg/hr**
- Give intermittent **Fentanyl 0.5-1 mcg/kg/hr** according to anesthesiologist in charge
- If Depth of anesthesia is not adequate or brain is tight, you can use **Propofol 2-6 mg/kg/hr** according to anesthesiologist in charge
- Assess **Hematocrit before PRC transfusion**, PRC is transfused when Hct.<27%
- 4 hours after skin incision Aspirate blood from A-line **3 ml** into heparin tube for assess Mg level
(Aspirate from vein if no A-line)

Intraoperative hypotension	Intraoperative hypertension
SBP<90 mmHg or decrease <20% from baseline	SBP>140 mmHg or increase >20% from baseline
1. Fluid resuscitation or 2. Vasopressor according to anesthesiologist in charge	1. Increase Sevoflurane to 1 MAC wait for 5 min, if BP still high 2. Fentanyl 25 mcg not exceed 2 times, wait for 5 minute (total 10 mins) if BP still high 3. Propofol intermittent bolus or continuous drip if depth of anesthesia is not adequate 4. If depth of anesthesia is adequate, Nicardipine 0.2-0.4 mg in titration or Labetalol 2.5-5 in titration or Continuous drip according to anesthesiologist in charge

End of the case

- **Stop Study drug when dura was closure**
- Discontinue muscle relaxant at least 30 minute before operation finish
- **Record Intraoperative blood loss (Primary outcome)**

Reversal and Extubation

- **Use Glycopyrrolate 0.4 mg and Neostigmine 2.5 mg as reversal agents**
- If residual neuromuscular blocking effect is suspected, evaluate train of four before extubation
- Extubation when patients fully awake, open eyes and follow command
- **Record time when fully awake and extubation (Secondary outcome)**
- If remain intubation, please note the reason for remaining intubation

Step for sending lab investigation

- Send heparin tube to laboratory within 2 hours
- 8.00 am – 4.00 pm contact research officer
- After 6.00 pm contact Dr.[name]

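### Does the plan need a rule for the awakening and extubation times of patients who stay intubated?

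*Protocol*

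**What the plan says.** Under the heading Reversal and Extubation the protocol sets the criterion, "Extubation when patients fully awake, open eyes and follow command", then gives the instruction "Record time when fully awake and extubation (Secondary outcome" and adds "If remain intubation, please note the reason for remaining intubation". It also foresees residual block: "If residual neuromuscular blocking effect is suspected, evaluate train of four before extubation".

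The opening narrative of the protocol expects two kinds of patient: "After the uneventful operation, the patients will be extubated and transferred to neurosurgical intensive care unit", and "Some patients will remain intubation and post-operative ventilation will be continued and reasons for remaining intubation will be noted". Its closing list of outcomes has blood loss, red cell transfusion, anaesthetic requirement and the postoperative cognitive score. Awakening and extubation times are not in it.

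Three events near the end of surgery could serve as time origin. Two come from the section End of the case: "Stop Study drug when dura was closure" and "Discontinue muscle relaxant at least 30 minute before operation finish". The third is the end of the operation itself. None is named as the origin.

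The SAP is one paragraph. It gives Student's t-test for continuous data that are normally distributed, the Mann-Whitney test otherwise, chi-square or Fisher's exact test for categories, and significance at p < 0.05. It does not mention missing or late times.

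**The concern.** Being fully awake is a condition for extubation. A patient kept intubated because of slow awakening could therefore lack a time because of the outcome itself. Analysing only those extubated in theatre would remove the slowest patients, more of them from the arm with the longer delay, and a null result could be misread as no delay.

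The other reading has its own difficulty. If later times are collected, a patient ventilated for many hours for surgical reasons enters with a value far from all the others, and the drug comparison might be swamped. With no stated choice between the two readings, and no time origin, two analysts could report different answers from the same trial. At stake is a secondary outcome bearing on recovery from anaesthesia.

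**Working it through.** **Inputs.** From the documents: 80 patients, two groups, blocks of 4, p < 0.05. Assumed: 1:1 allocation (40 per arm), two-sided tests, and every retention rate and time distribution, since the documents give none. The plan has no figure of its own to reproduce for this outcome. Rates are written saline v magnesium. Log-time is taken as normal with SD 1, and power comes from 10,000 simulated trials per scenario.

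**1. Patients retained for slow awakening are dropped.** Let everyone beyond a common cut-off be retained, a share p on saline and q on magnesium. With z(·) the normal quantile and φ the normal density:

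- true delay d = z(1−p) − z(1−q)
- delay shown after dropping = d − φ(z(1−q))/(1−q) + φ(z(1−p))/(1−p)

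For 5% v 20%: d = 1.645 − 0.842 = 0.803. Shown = 0.803 − 0.280/0.80 + 0.103/0.95 = 0.56 SD.

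For 2% v 5%: d = 2.054 − 1.645 = 0.409. Shown = 0.409 − 0.103/0.95 + 0.048/0.98 = 0.35 SD.

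| Retained | True delay (SD) | Shown (SD) | Power, dropped | Power, longest rank |
|---|---|---|---|---|
| 2% v 5% | 0.41 | 0.35 | 36% | 42% |
| 1% v 5% | 0.68 | 0.60 | 78% | 84% |
| 5% v 20% | 0.80 | 0.56 | 77% | 93% |

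The direction is as feared. The loss is about 6 points of power at low rates and becomes large only if one patient in five on magnesium is retained for slow awakening.

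**2. Later times are kept, retention is surgical.** Ranks are bounded, so the length of ventilation does not matter. The rank sum of 80 patients is 80 × 81/2 = 3240. The top 4, 8 or 16 patients hold 314, 612 or 1160 of it, that is 9.7%, 18.9% or 35.8%. In one simulated data set the Mann-Whitney p-value was 0.0315 whether ventilation lasted 120, 600 or 2880 minutes.

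With a true delay of 0.80 SD and equal surgical retention, power with these patients left out against ranked at their later times is 90% v 78% at 10% per arm and 86% v 56% at 20% per arm. That is dilution. The t-test does collapse, to about 5% power. But the SAP reserves it for normally distributed data, and times with a few values of many hours are not normal, so the SAP's own rule leads to Mann-Whitney.

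**3. False rejection.** With no delay and equal surgical retention of 10%, 15% or 20%, ranking the later times rejects in about 5% of trials. A rate of 12% arises only if true retention is 20% in one arm and 10% in the other. Under randomisation, such a difference would itself be an effect of treatment.

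**4. Both kinds of retention, 10% surgical per arm (Mann-Whitney power).**

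| Slow awakening | Drop all retained | All at later times | Leave out surgical only |
|---|---|---|---|
| 1% v 5% | 73% | 64% | 79% |
| 5% v 20% | 71% | 78% | 90% |

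Neither simple choice is better throughout: dropping everyone wins in the first row, keeping everyone in the second. Leaving out only surgical cases wins in both but depends on the recorded reason. With 25% of reasons wrong it gives 75% and 85%; with 50% wrong, 70% and 78%, so in the first row it falls below dropping everyone.

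**The case for a change.** The strongest case for acting is that the fix looks cheap and the ambiguity is real. Slow wakers may be missing because of what is being measured. Comparing the numbers retained is a weak safeguard: Fisher's exact test has 1% power at 1% v 5% and 41% at 5% v 20%, and 2/40 v 8/40 gives p = 0.087. A few sentences in the SAP would close a free choice between analyses.

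What stands is that the rule is absent, the time origin is absent, and the two outcome lists differ. What does not follow is that the plan goes wrong. The instruction to record the times carries no exception for retained patients. The line about the reason adds to it, and nothing says these patients are dropped. The reason is on record, so counts by arm and reason can be reported beside the times. The trial is double-blind, so analysts can fix the origin and the handling before they know the arms. The differing lists are an editorial mismatch.

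The only substantive rule on offer is to leave surgical retention out of the main comparison. The protocol ties extubation to an uneventful operation, and the trial asks whether magnesium changes blood loss. If it does, surgical retention may depend on treatment, and excluding those patients after randomisation could add bias in return for power. Keeping everyone respects randomisation and costs power. Either choice is defensible.

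**Conclusion.** No change to the plan is called for. The gap is real but minor, and it lies in detail that a competent analyst supplies: an origin for the clock, later times where they exist, and a count of patients left intubated by arm and reason. The Mann-Whitney and Fisher tests needed are already in the SAP.

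The possible loss from dropping retained patients runs from about 6 points of power at 2% v 5% to about 16 points at 5% v 20% (77% v 93%). Every one of those rates is an assumption. Keeping later times dilutes the rank test without raising false rejection under equal retention. No rule stated in the documents is shown to give a wrong answer. In reading the results, a null comparison among extubated patients alone should not be taken as evidence of no delay. The conclusion assumes 40 per arm, a rank-based comparison when times are clearly skewed, and handling settled before unblinding.

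### The bedside sheet lets the only post-dose magnesium tube wait up to 2 hours and omits the 4 mg/dl stop rule, so the safety stop can act late or not at all

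*Protocol*

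**What the plan says.** The protocol narrative gives the regimen as "40 mg/kg of magnesium sulphate loading in 30 minutes at incision and then continuous drip 10 mg/kg/hr until dura will be closure". On monitoring it says "Magnesium level will be measured at beginning and 4 hours", and then "If magnesium level is more than 4 mg/dl, study drug will be stopped".

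The bedside sheet ties the second draw to incision under Maintenance: "4 hours after skin incision Aspirate blood from A-line". Its equipment list provides two heparin tubes, which matches one baseline and one post-dose sample. Under the step for sending laboratory samples, both tubes share one instruction: "Send heparin tube to laboratory within 2 hours". Two contact lines follow: "8.00 am – 4.00 pm contact research officer" and "After 6.00 pm contact" a named person.

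The sheet does not mention the 4 mg/dl limit. Under End of the case it ties stopping study drug to dural closure only. Neither the narrative nor the sheet gives a laboratory turnaround time, pauses the infusion while the result is pending, or says who receives the result and passes it to theatre. The SAP is silent on all of this.

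**The concern.** A rule that stops a running infusion works only if its trigger arrives while the infusion is still running. Here the trigger is a single result. The staff at the bedside work from a sheet that sets a 2-hour outer limit for sending the tube, does not mark the 4-hour tube as needed for a decision during the operation, and does not show the limit the result is to be compared with. A team could follow the sheet exactly and still leave the narrative's safety rule without effect.

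At stake is the safety of a patient who is already above the protocol's own limit and continues to receive magnesium. A related question arises at baseline. A starting magnesium above 2.6 mg/dL is an exclusion, yet the only baseline draw described is taken in theatre after induction, and dosing starts at incision. The same 2-hour allowance could let that result arrive after dosing has begun.

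**Working it through.** **Inputs.** From the narrative: loading dose 40 mg/kg over 0.5 h from incision; maintenance 10 mg/kg/hr until dural closure; stop limit 4 mg/dl. From the bedside sheet: second draw at 4 h after incision; tube sent at any time up to 2 h after that; pump settings of 0.2 ml/kg for loading and 0.05 ml/kg/hr for maintenance.

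**Step 1: reproduce the sheet's pump example (60 kg).**
- Loading volume: 0.2 × 60 = 12 ml. Rate: 12 / 0.5 = 24 ml/hr.
- Maintenance: 0.05 × 60 = 3 ml/hr.
- Implied concentration: 40 / 0.2 = 200 mg/ml and 10 / 0.05 = 200 mg/ml.

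The example is reproduced, and the narrative and the sheet describe the same dose.

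**Step 2: dose given by time t (hours after incision, t ≥ 0.5, dura open).** Dose = 40 + 10 × (t − 0.5) mg/kg.
- At the draw, t = 4: 40 + 35 = 75 mg/kg.
- At the end of the sending allowance, t = 6: 40 + 55 = 95 mg/kg.
- Difference: 20 mg/kg, which is 20 / 75 = 26.7% of the dose given by the draw. At 60 kg this is 20 × 60 = 1,200 mg, or 3 × 2 = 6 ml.

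**Step 3: add laboratory time.** The documents give none. As an assumption only, take L = 0.5 to 2 h from sending to result. Extra dose after the draw = 10 × (sending delay + L) mg/kg.

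| Sending delay | Earliest stop after incision | Extra dose after the draw | At 60 kg |
|---|---|---|---|
| 0 h | 4.5 to 6 h | 5 to 20 mg/kg | 0.3 to 1.2 g |
| 2 h (permitted maximum) | 6.5 to 8 h | 25 to 40 mg/kg | 1.5 to 2.4 g |

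Whatever L is, the part due to the sending allowance is 20 mg/kg (25 − 5 and 40 − 20).

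**Step 4: when the rule cannot act.** If the dura closes before 4 h, the infusion has already ended at the draw. If it closes between the draw and the result, the rule has nothing left to stop. The documents give no operating times, so the share of patients in each case cannot be calculated.

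**Step 5: contact list.** A 4-hour draw falls between 16:00 and 18:00 when incision is between 12:00 and 14:00. With the full 2-hour allowance, draws from 14:00 to 16:00 (incision 10:00 to 12:00) can also be sent in that period.

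**The case against.** The strongest reply is that nothing here is a formal contradiction. A draw at 4 hours, sending within 2 hours and a stop above 4 mg/dl can all hold together. The 2 hours is a maximum that fully allows sending at once, and it may be a sample-stability limit. That stands as far as it goes: the delay is the permitted worst case, and a reader who inferred that the plan intends or expects a stop hours late would go beyond the text. It does not remove the point, because a stability limit does not tell staff that the result is needed during the operation, and no other line on the sheet does.

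Two further readings are tempting and unsupported. One is that a patient's magnesium exposure would be 27% too high. The figure is administered dose, whereas the limit concerns serum level. The documents give neither expected levels nor the chance of exceeding 4 mg/dl, and they exclude patients with renal insufficiency or a raised starting magnesium. The other is that the contact gap delays the result. The sheet does not say what the contacts are for or that sending depends on reaching one, and one of the two times may be a typing slip. The gap is worth correcting but is not shown to cause delay.

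It can also be said that this is clinical management. The sampling time, dose and threshold are, and they are not questioned here. Whether the sheet's handling steps allow the narrative's rule to operate is a matter of consistency within the protocol.

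**Conclusion.** The point holds as a worst case that the text permits. The stop rule depends on one post-dose result. The sheet lets that tube wait up to 2 hours while the infusion continues, and it omits the rule itself. The result may then come no earlier than 6 hours after incision, plus laboratory time. The sending allowance accounts for at most 20 mg/kg of further administered dose (75 to 95 mg/kg; 1.2 g at 60 kg).

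This applies only to a magnesium-arm patient whose level is above 4 mg/dl, whose tube waits the full allowance, and whose dura stays open throughout. The number of such patients is unknown. The arithmetic assumes that the stated infusion rates run without interruption. The absence of the 4 mg/dl rule from the sheet matters as much as the sending time, since a prompt result does not help if those at the bedside are not told what to do with it. The change should be made because it concerns safety and costs little.

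**What to change.** Ask the sponsor to reconcile the narrative's stop rule with the bedside sheet:

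1. Reconcile the 2-hour sending allowance with the stop rule, so that the handling of the 4-hour tube lets its result arrive while the infusion can still be stopped.
2. Carry the narrative's 4 mg/dl rule onto the bedside sheet, beside the dural-closure instruction.
3. State who receives the result and how a stop is communicated. The trial is double-blind and anesthetic requirement is an outcome, so the treating anesthesiologist should not be unblinded more than the stop requires.
4. Check the same allowance for the baseline tube against the exclusion for magnesium above 2.6 mg/dL, given that dosing starts at incision.
5. As a minor correction, close or correct the gap between 4.00 and 6.00 pm in the contact list.

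Sampling time, dose and threshold remain the sponsor's decision. The cost is a few lines of text and no additional samples. Item 5 may mean naming someone for 4 to 6 pm; the documents do not show whether a person is already available then.

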**The effects of magnesium sulphate on intraoperative
blood loss in meningioma patient undergoing
craniotomy with tumor removal: A prospective
randomized study.**

NCT number: NCT03558516

Document date: 1 August 2018

Statistical Analysis Plan

The collected data will be analyzed by Statistical Package for the Social Sciences (SPSS) software version 18.0 (SPSS Inc., Chicago, IL, USA). Data will be described in terms of frequencies (number and percent of cases), mean \pm standard deviation, median (range) when appropriate. Chi-square or Fisher's exact test will be used for comparing categorical data. Student's t-test will be used for comparing continuous data with normal distribution. Comparison of nonparametric variables will be done using Mann-Whitney test. The p-value < 0.05 will be considered statistical significance.

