**The effects of magnesium sulphate on intraoperative
blood loss in meningioma patient undergoing
craniotomy with tumor removal: A prospective
randomized study.**

NCT number: NCT03558516

Document date: 1 August 2018

Study protocol

The protocol was approved by the institutional ethics committee (SI 259/2018). After obtaining written informed consent from all patients, a randomized double-blinded placebo-controlled trial was conducted on 80 patients. This study was registered at Clinical Trials.gov (NCT03558516). The patients will be randomized into 2 groups in blocks of 4 by computer-generated numbers. The sequence numbers and groups will be placed inside concealed envelopes, which will be opened by researchers. The researchers will enroll the participants but will not take part in patient care.

We will enroll patients aged between 18-70 years, American Society of Anesthesiologist (ASA) grade I and II, diagnosed of supratentorial meningioma and underwent craniotomy with tumor removal at Siriraj hospital, Mahidol university. The exclusion criteria included all of the following conditions; preoperatively unstable hemodynamics requiring vasopressors or vasodilators, heart disease or heart block, liver disease Child Pugh Score C, Renal insufficiency or estimated glomerular filtration rate (e-GFR) < 60 mL/min, allergy history of magnesium or any drug use in study protocol, use calcium channel blocker before operation, pregnancy, receive magnesium sulfate to treatment other conditions, baseline serum magnesium more than 2.6 mg/dL, BMI > 30 kg/m², and prone to brain herniation from increased intracranial pressure.

On the day before surgery, the informed consent will be obtained and baseline cognitive function will be measured by Montreal Cognitive Assessment (MOCA) test.

At the operating room, standard monitorings will be used. General anesthesia will be inducted with propofol 1.5-2.0 mg/kg, fentanyl 1-2 mcg/kg, and then cis-atracurium 0.15 mg/kg will be given for facilitating tracheal intubation. Then, the extra-large bore intravenous lines will be accessed and radial artery will be cannulated for continuous arterial pressure monitoring. A baseline blood sampling for magnesium level will be obtained.

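### The SAP prespecifies no use of baseline MOCA when postoperative MOCA is compared, so this non-primary comparison gives up available precision

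*SAP*

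**What the plan says.** The narrative part of the Protocol states that, on the day before surgery, "baseline cognitive function will be measured by Montreal Cognitive Assessment (MOCA) test". The second test "will be done at postoperative day 3-7 when patient has less pain and recover enough for comfortable testing". The list of outcomes that closes the narrative ends with "anesthetic requirement and postoperative MOCA score". It names the postoperative score itself, not a change from baseline or an adjusted score. In the working protocol, under End of the case, blood loss is labelled primary and time to full awakening and extubation is labelled secondary. MOCA carries neither label.

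The SAP is a single paragraph. Student's "t-test will be used for comparing continuous data with normal distribution", and the Mann-Whitney test covers what it calls nonparametric variables. It names no covariate, regression model, change score or paired analysis, and it does not mention MOCA. Its opening rule on descriptive statistics would cover a summary of baseline MOCA, but nothing in either document gives that score a role in comparing the groups.

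**The concern.** A patient's cognitive score shortly after surgery is likely to depend in part on the score before it. In a t-test or Mann-Whitney test of the postoperative score alone, the spread between patients that was already there before the study drug stays in the error term. The confidence interval is then wider, and the power lower, than the collected data require.

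This is a loss of precision, not a bias. Over repeated randomisations the unadjusted difference is unbiased and its type I error is 5%. In the one trial that is run, however, a chance imbalance in baseline MOCA carries over into the postoperative difference in proportion to the pre/post correlation, and the planned tests do nothing about it. What is at stake is the MOCA conclusion alone.

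The silence also leaves raw score, change score and adjusted score all open, so the choice could be made after the data are seen.

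**Working it through.** **Inputs from the documents**
- Sample size: "a randomized double-blinded placebo-controlled trial was conducted on 80 patients" (Protocol, narrative).
- Allocation: "The patients will be randomized into 2 groups in blocks of 4 by computer-generated numbers". The ratio is not written out; 1:1, so n = 40 per arm, is assumed.
- Significance: "The p-value < 0.05 will be considered statistical significance" (SAP). Sidedness is not stated; two-sided is assumed.

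**Inputs not in the documents.** The pre/post correlation r, the SD of MOCA, a target difference and the number of completers are not given. I take r = 0.3, 0.5, 0.7 and 0.8, work in SD units, use 0.5 SD as an illustrative difference, and show both 40 and 35 completers per arm.

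**The plan's own figure.** The total of 80 cannot be reproduced, because no effect size, SD or power is stated for any outcome. As a benchmark, with 40 per arm the unadjusted t-test has 80% power to detect 0.634 SD (non-central t).

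**Formulas**
- Error variance after adjustment: multiplied by 1 − r².
- Equivalent unadjusted total: 80/(1 − r²). At r = 0.5 this is 80/0.75 = 106.7.
- 95% CI half-width: t × √[(2/40)(1 − r²)], with √(2/40) = 0.2236 and t = 1.991. Unadjusted, 1.991 × 0.2236 = 0.445 SD. At r = 0.5, 0.445 × √0.75 = 0.386 SD.
- Power: non-central t with non-centrality 0.5/[0.2236 × √(1 − r²)], on 78 df unadjusted and 77 df adjusted. Unadjusted, 0.5/0.2236 = 2.236. At r = 0.5, 2.236/0.866 = 2.58.
- SE of the part of a chance baseline imbalance that carries into the unadjusted difference: r × 0.2236.

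| | Unadjusted | r = 0.3 | r = 0.5 | r = 0.7 | r = 0.8 |
|---|---|---|---|---|---|
| Variance factor | 1 | 0.91 | 0.75 | 0.51 | 0.36 |
| Equivalent total N | 80 | 87.9 | 106.7 | 156.9 | 222.2 |
| CI half-width (SD) | 0.445 | 0.425 | 0.386 | 0.318 | 0.267 |
| Power at 0.5 SD, 40 per arm | 0.598 | 0.639 | 0.722 | 0.871 | 0.957 |
| Power at 0.5 SD, 35 per arm | 0.541 | 0.580 | 0.663 | 0.823 | 0.930 |
| Detectable difference at 80% power (SD) | 0.634 | 0.605 | 0.549 | 0.453 | 0.381 |
| Carried-over SE (SD) | – | 0.067 | 0.112 | 0.157 | 0.179 |

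**Simulation checks.** With bivariate normal scores, ANCOVA power at 0.5 SD was 0.633, 0.719, 0.868 and 0.955, close to the table. Under the null, overall type I error was 0.05 for both methods. Conditional on the baseline difference the methods part. In the 7% of null trials with an imbalance of at least 0.4 SD, the t-test rejected in 0.09, 0.16, 0.27 and 0.35 of trials at the four values of r. In the other 93% it rejected in about 0.048, 0.039, 0.032 and 0.026, which is why the overall rate is right. ANCOVA stayed at about 0.05 in the imbalanced subset.

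**The Mann-Whitney branch.** In a simulation of a bounded, rounded MOCA-like score, rank-based ANCOVA had power of about 0.60, 0.69, 0.83 and 0.92, against about 0.57 for Mann-Whitney. The gain is not confined to the t-test.

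**Change score instead.** Its variance factor is 2(1 − r): 1.4, 1.0, 0.6 and 0.4. At r = 0.3 that is worse than ignoring baseline, and ANCOVA has the smaller factor at every r shown.

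**Cost if r is low.** Estimating one covariate adds about 1/76 = 1.3% to the variance. ANCOVA breaks even when (1 − r²)(77/76) = 1, that is r² = 1/77, or r of about 0.11.

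**The case against.** The strongest reply is that nothing here is wrong. The SAP's tests are valid for the outcome as the Protocol names it, and the documents do not contradict each other. MOCA comes last in the outcome list, is labelled neither primary nor secondary, and has no target difference or power claim. That stands, and it limits the point to an improvement in efficiency.

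Second, the size rests wholly on assumed values. The range runs from almost nothing to very large, and below r = 0.3 it shrinks further: power is 61.6% at r = 0.2 and 60.2% at r = 0.1, against 59.8% unadjusted. A low r is plausible, because the test day varies from 3 to 7 and depends on recovery. This also stands: the omission is certain, its size is not. But the possible loss from adjusting is about 1% in variance, while the possible gain is large.

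Third, carry-over of r times the imbalance holds only in SD units with equal SDs before and after surgery; in general it is the regression slope times the imbalance. That is correct, and it does not alter the remedy.

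Fourth, the t-test could be applied to a change score. The SAP does not say so, the named outcome is the postoperative score, and a change score is the weaker use of baseline at each r shown.

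**Conclusion.** The concern holds. A baseline MOCA is planned, and no prespecified comparison uses it. At a moderate correlation of 0.5, adjustment would be worth about 27 extra patients (106.7 − 80) for the MOCA comparison and would raise power for a 0.5 SD difference from 60% to 72%. At r = 0.3 the gain is small (64%); at r = 0.7 or 0.8 it is large (87% or 96%). These figures assume 1:1 allocation, 40 completers per arm, a two-sided 5% test and roughly normal scores. With 35 completers per arm the same pattern holds from a lower start (54% unadjusted). The unadjusted test remains valid and the primary blood-loss conclusion is untouched, so this is a change worth making, not a flaw that undermines the trial.

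**What to change.** Add to the SAP:

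1. The main MOCA analysis is ANCOVA of postoperative MOCA on treatment group with baseline MOCA as covariate, reporting the adjusted mean difference and its 95% CI.
2. A rank-based ANCOVA (ranked postoperative score on group and ranked baseline score) is a sensitivity analysis, reported whatever the residuals look like. It supplies a test, not a mean difference.
3. The number of patients per arm with both MOCA tests is reported, and the SAP says what is done with a patient who lacks only the baseline test. ANCOVA in completers does not correct for who was well enough to be tested, so these counts are needed to read the result.

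The cost is a few sentences and a standard general linear model procedure in SPSS. No new data are needed, and nothing changes in patient care or in the blood-loss analysis.
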